## 7.9.2 Secondary Objective

The secondary objectives are intended to gain additional information about the safety and performance of surgical products. There will be no established performance goals related to the secondary objectives.

All the variables included in the secondary objective will be summarized overall and/or by group if applicable using descriptive statistics. For survival outcomes, Kaplan-Meier method will be used to estimate survival probability. The calculated survival probability at a given time  $t$  is an estimator of survival probability beyond  $t$ , conditional on survival prior to the time  $t$ . The 2-sided point-wise 95% confidence limit will be calculated using the log-log transformation.

Mortality will be calculated. The causes of death and relatedness of death to surgical or medical procedure and/or the product(s) will be summarized in a table. All deaths will be listed.

Device deficiencies (DD) will be summarized by MedDRA terms and product type. All the device deficiencies will be listed.

Product related adverse events will be summarized by MedDRA terms and product type. The number of events and the number and percentage of subjects who experienced the event will be reported.

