- Surgical History
- Vital signs
- Quality of Life or satisfaction measurements, if applicable

B.3 Procedure

The following types of data may be collected for enrolled patients as applicable for the procedure performed:

- Perioperative details
- Device details
- Adverse Events, Device Deficiencies, Deaths, and deviations are to be reported to Medtronic upon awareness
- Imaging, if applicable
- Procedure recordings, if applicable
- Quality of Life or satisfaction measurements, if applicable

[figure not shown]
[figure not shown]
B.4 Follow-up Reporting Frequency & Data Collection

Patients will be treated in accordance with the routine clinical practices of their respective care provider. However, in 'real world' clinical practice, the frequency of in-person follow-up visits may vary for many reasons (e.g., patient's personal circumstances, condition, physician preference, etc.) resulting in more or fewer in-person visits.

As a result, the PSR is based on an active surveillance model which requires sites to complete a patient status assessment post-procedure, regardless of whether the patient is seen in-person per the physician's routine follow-up care practices. This approach ensures a robust dataset while increasing the continual awareness of patient status throughout their registry participation.

Data will be captured through 30 days post-procedure (to be reported between day 30 and 37) at a minimum and may be captured up to 60 months (or 5 years) post-procedure (Figure 1).

For procedures requiring long-term follow-up data, assessments will be collected at least annually with a maximum follow-up duration of 60 months at which time the patient will be exited (Figure 1). The total duration of follow-up for products requiring long-term follow-up data collection will be determined by various factors including but not limited to product lifecycle, recurrence rate, or regulatory requirements. The timing of the patient assessments and exit will be outlined in the corresponding Analysis Plan or Addendum. Refer to Figure 2 for an example of a long-term follow-up data collection schedule.

Surgical Appendix - Figure 1: Follow-up Schedules**Surgical Appendix - Figure 2: Example of a Long-term Schedule**

Follow-up data will be collected for enrolled patients and may include, but are not limited to:

- Patient status
- Readmissions
- Imaging information, if applicable
- Procedure recordings, if applicable

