- Quality of Life or satisfaction measurements, if applicable
- Adverse Events, Device Deficiencies, Deaths, reinterventions, and deviations are to be reported to Medtronic upon awareness

B.5 Events

All procedure or device related events are to be reported upon site awareness. Submit any additional supporting evidence which could assist in the assessment and review. Further supporting evidence not originally provided by the site may be requested by Medtronic to aid in the adjudication of the event.

Refer to Table 1 below for Unavoidable Adverse Events, which if resolved within the timeframe specified, are **not** required to be reported.

Surgical Appendix - Table 1: Unavoidable Adverse Events

Event Description	Time Frame (hours) from end of Procedure
Anesthesia related nausea / vomiting/ headache	24 hours
Low-grade fever (<100°F or < 37.8°C)	48 hours
Pain at Access Site	72 hours
Mild to moderate bruising / ecchymosis at access site	168 hours (7 days)
Back pain related to lying on the table	72 hours
Constipation	72 hours
Postoperative pain and/or complications that the Investigator considers common and within normal limits for the procedure and its related medication.	

Refer to Table 2 below, for a listing of potential **reportable** Adverse Events. The listing is provided to facilitate more complete and consistent reporting and is not intended to be a comprehensive listing of all reportable events.

Patients with adverse events that have not resolved at the time of the final registry timepoint will be followed until resolution, for up to 30 days after the final registry timepoint, or other applicable period as defined in the analysis plan or addendum.

Surgical Appendix - Table 2: Potential Reportable Adverse Events

Allergic reactions	Inflammatory reaction	Seroma
Bleeding/hematoma	Inadvertent injuries to other tissues or organs	Thromboembolic complications
Blood transfusion	Nerve damage	Vascular injury
Cardiopulmonary complications	Nerve entrapment	Visceral adhesions
Chronic pain	Hernia Recurrence	Visceral injuries
Damage to pericardium	Renal failure	Wound dehiscence
Infection	Respiratory complications	

The site will report the clinician's assessment of an adverse event relative to relatedness (e.g., device or procedure), seriousness and severity. The definitions for seriousness and relatedness can be found in section 12.1, Table 2: Adverse Event and Device Deficiency Definitions. The definitions for severity are in Table 3 below.

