### 4.2 Secondary Objective

The secondary objectives are intended to gain additional information about safety and performance of the products for surgical innovations and surgical robotics. There are no established performance goals related to the secondary objectives.

For products following the short-term schedule, the following variables/outcomes will be evaluated to gain additional information, but are not limited to:

- Procedure details including intra- and post-operative assessments
- Incidence of specific events during or post procedure

- Mortality
- Length of hospital stay
- Readmission rate
- Reintervention rate
- Product related events
- Device deficiencies (DD)

For products following the long-term schedule, in addition to the variables/outcomes listed above, the overall survival, study-specific survivals may be carried out for safety and performance evaluation.

This SAP intends to cover the objectives specified above. For any objectives described in the study protocol or addendum, but not listed here, they will be included in study-specific SAP addendum. Please refer to study-specific SAP for the details regarding primary and secondary objectives if they are not included in this SAP.

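### SAP 7.9.2 sets Kaplan-Meier for every survival outcome without a rule for death; for a non-fatal event analysed with deaths censored, one minus Kaplan-Meier would overstate incidence

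*SAP*

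**What the plan says.** SAP 4.2 adds time-to-event outcomes for products on the long-term schedule only: "the overall survival, study-specific survivals may be carried out for safety and performance evaluation". The study-specific survivals stand beside overall survival, so they are something other than death from any cause, but they are not defined. SAP 7.9.2 gives one method for all of them: "For survival outcomes, Kaplan-Meier method will be used to estimate survival probability", with point-wise 95% limits on the log-log scale.

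The rest of the secondary list is handled differently. SAP 7.9.2 says "All the variables included in the secondary objective will be summarized overall and/or by group if applicable using descriptive statistics", and SAP 4.2 lists "Reintervention rate" as one of those variables, not as a survival outcome. The primary event rate (SAP 7.9.1.3) is a count divided by units, with a binomial interval.

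In the protocol, Surgical Appendix B.4 sets "a maximum follow-up duration of 60 months at which time the patient will be exited". It says the length of long-term follow-up depends on factors "including but not limited to product lifecycle, recurrence rate, or regulatory requirements". Appendix Table 2 (B.5) lists "Hernia Recurrence" as a potential reportable event. Protocol 10.12 makes death a reason for exit. Neither document gives a censoring rule, a role for death in the survival analyses, or a competing-risk method.

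**The concern.** Kaplan-Meier is the right estimator when death is the event or part of it. When the event is non-fatal and death is treated as censoring, 1-KM estimates the risk in a hypothetical population in which nobody dies first. It does not estimate the share of treated patients who actually have the event.

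The registry's stated purpose is real-world performance and patient outcomes (Protocol 4.2 and 5.1), and that share is the natural quantity to report for it. A non-fatal long-term endpoint is foreseeable, because recurrence helps to set the follow-up length and reinterventions are collected throughout. As the SAP stands, two teams could define the same 5-year endpoint, handle death differently and both comply. A team that chose a competing-risk estimator would have to justify it as a departure from the plan.

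**Working it through.** **The plan's own figures.** The only computed figures in the documents are in the sample-size table of SAP 6.1. All nine cells reproduce when rounded up; for example, a 10% rate with a 5% half-width gives 1.96² × 0.10 × 0.90 / 0.05² = 138.30, so 139. That table concerns the primary binomial rate and does not depend on Kaplan-Meier. The plan gives no figure for a survival outcome, so what follows is illustrative.

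**Inputs.**
- Horizon of 5 years: the 60-month maximum in Surgical Appendix B.4.
- 5-year 1-KM (*e*) of 5%, 10% and 20%: an assumption, borrowed from the 5% to 20% range of event rates in SAP 6.1.
- 5-year mortality (*d*) of 1% to 40%: an assumption, since the documents give none.
- Independent, constant hazards for the event and for death: an assumption.

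**Formulas.**
- Hazards: λe = −ln(1−e)/5 and λd = −ln(1−d)/5.
- Death censored: 1-KM at time t = 1 − exp(−λe·t), which is *e* at 5 years. It does not contain λd.
- Cumulative incidence with death competing: CIF(t) = λe/(λe+λd) × [1 − exp(−(λe+λd)·t)].

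**Worked cells.** For e = 10% and d = 20%, λe = 0.02107 and λd = 0.04463. Their sum is 0.06570 and the ratio is 0.3207. The bracket is 1 − 0.9 × 0.8 = 0.28, so CIF = 0.3207 × 0.28 = 8.98%. For e = d = 20%, the ratio is 0.5 and the bracket is 1 − 0.8 × 0.8 = 0.36, so CIF = 18.0%.

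**Results at 5 years: cumulative incidence (overstatement by 1-KM, in percentage points).**

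| Assumed mortality | 1-KM 5% | 1-KM 10% | 1-KM 20% |
|---|---|---|---|
| 1% | 4.98% (0.02) | 9.95% (0.05) | 19.90% (0.10) |
| 5% | 4.88% (0.13) | 9.75% (0.25) | 19.51% (0.49) |
| 10% | 4.75% (0.25) | 9.50% (0.50) | 19.02% (0.98) |
| 20% | 4.49% (0.51) | 8.98% (1.02) | 18.00% (2.00) |
| 40% | 3.92% (1.08) | 7.87% (2.13) | 15.81% (4.19) |

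The relative overstatement runs from about 0.5% at 1% mortality to about 27% at 40%.

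**Checks.**
- A simulation of 400,000 patients with e = 10% and d = 20% gave a 1-KM of 10.03% and a cumulative incidence of 9.01%, in line with the formulas.
- With the same hazards, the gap at 1 year is at most 0.21 points across the grid, and at 30 days it is negligible.
- If death counts as an event, Kaplan-Meier estimates the composite without this bias. In the 10%/20% case the composite is the 28% shown above.

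**The case against.** The strongest reply is that the SAP never says deaths are censored. It gives no event definition and no censoring rule, and exit at death under Protocol 10.12 is an administrative rule, not an analysis rule. Event-free survival with death as an event fits the text equally well, and Kaplan-Meier is correct for it. That stands, so the point is conditional.

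Three stronger readings are tempting, and the documents do not support them.
- *Recurrence and reintervention figures will be biased upward.* Reintervention is a descriptive rate, and recurrence is never named as a survival endpoint. Related adverse events feed the primary rate, a crude proportion that this mechanism cannot inflate.
- *All long-term event probabilities are overstated.* Overall survival and composites that include death are unaffected, and the survival analyses are optional.
- *High-mortality cohorts look worse under Kaplan-Meier.* In the model above, 1-KM does not depend on mortality. With equal event hazards it leaves the cohorts equal, and it is the cumulative incidence that falls as mortality rises.

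The last item also shows that a Kaplan-Meier freedom-from curve has a legitimate use as a display of product reliability. Which quantity should lead is partly a matter of choice.

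It can also be said that a study-specific addendum would settle these matters. This is only a partial answer. SAP 3 says that an objective outlined in the SAP will be analysed as the SAP describes. SAP 4.2 counts study-specific survivals among the objectives covered, and it reserves the addendum for what is not covered. SAP 3 says only that such an addendum may be written. Kaplan-Meier is therefore the default.

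**Conclusion.** The point holds as a gap in specification with a conditional bias. SAP 7.9.2 fixes Kaplan-Meier for every survival outcome, including study-specific ones that are left undefined, and neither document says what happens to deaths. If such an outcome is a non-fatal event alone, deaths are censored, and 1-KM is read as the proportion of patients affected, that proportion is overstated.

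Under the assumed constant hazards, the 5-year overstatement ranges from 0.02 to 4.19 percentage points over the grid. It is small at low mortality and material only where 5-year mortality is substantial: 1.02 points on 10% and 2.00 points on 20% when mortality is 20%. The documents give no mortality figure, so no single value can be assigned to any cohort. The primary event rate, overall survival and 30-day results are not materially affected. The outcomes at issue are optional, secondary and free of hypotheses or performance goals, so this is a modest correction to the plan.

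**What to change.** Amend SAP 7.9.2 as follows:
- Keep Kaplan-Meier with log-log limits for overall survival and for composites that count death as an event.
- For any survival outcome defined by a non-fatal event alone, report the Aalen-Johansen cumulative incidence with death as a competing event and point-wise 95% limits. Show the Kaplan-Meier freedom-from curve as a supplementary display, labelled as treating death as censoring.
- Require the SAP or its addendum to state, for each study-specific survival, the time origin, the event, the censoring rules and the role of death.

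The cost is a few sentences of SAP text and a standard software option. No new data are needed, because deaths are already reported on site awareness (Protocol 10.8; Surgical Appendix Table 4). The downside is less direct comparability with any earlier reports based on Kaplan-Meier, which showing both curves resolves. Because cumulative incidence falls as mortality rises, comparisons between cohorts should be read alongside mortality and the supplementary curve.

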## 7.10 Safety Evaluation

Safety evaluation, such as the surgical or medical procedure related events, product related events, and device deficiencies will be summarized and listed as appropriate. Patient death will also be summarized and listed. Refer to 7.9 Evaluation of Objectives for details.

## 7.11 Changes to Planned Analysis

Any deviation from the analyses described in the statistical analysis plan and a justification for making the change will be documented in the final report if applicable or relevant study summary.

## 8. Validation Requirements

To ensure the quality of the statistical results and datasets created for the study, the following validation requirements will be implemented. Programs that contribute directly or indirectly to results pertaining to the primary objective including ADaM datasets and TLGs (Tables, Listings, and Graphs) development will be validated at level I or level II by a statistician or a statistical programmer. For the secondary objective, at least level II validation will be applied. Level III validation may be used for any previously validated program where only minor/administrative changes were made (e.g., change the location of the data directory). Any results that are used for external publication and reports should be validated at level I or Level II.

